## **PROTOCOL SYNOPSIS**

Protocol Title:	The Effect of Lysulin on Glycemic Control and Advanced Glycation in Inadequately Controlled Type 2 Diabetes Mellitus: A Double blinded Placebo Controlled Study
Site Numbers & Names:	Phoenix VA Health Care System
Research Hypothesis:	Dietary supplement (Lysulin™) reduces blood glucose, hemoglobin A1c and Advanced Glycation Endproducts in individuals with inadequately controlled type 2 diabetes.
Study Schema: Drugs / Doses / Length of Treatment)	Lysulin 3,330 mg/d (two 555mg tablets TID) x 12 weeks
Study Objectives: 

• Primary:

• Secondary:

	The primary objective is to determine whether 12 weeks of treatment with Lysulin, compared to placebo, causes a reduction from baseline in the plasma levels of glucose, hemoglobin A1c (HbA1c) and Advanced Glycation End products (AGEs) in patients with inadequately controlled type 2 diabetes mellitus. Secondary objectives include determining whether 12 weeks of treatment with Lysulin increases beta-cell function as measured by plasma C-peptide levels.
Study Design	This is a randomized, prospective, double-blind study. Randomization to Lysulin and placebo will be in a 1:1 fashion.
Accrual Goal: (Total number of subjects)	60 subjects for the successful completion of 56 subjects
Accrual Rate: (Number of subjects expected per month)	15 subjects/month
Correlative Studies: (PK/PD, etc.)	N/A
Inclusion Criteria:	
 
1. Signed written informed consent
 
2. Able to communicate meaningfully with the investigator and legally competent to provide informed written consent
 
3. Men and women, ages 21-75 years
 
4. Diabetes, with HbA1c <math>\geq</math> 7.5 % and <math><</math> 10% within 6 weeks of screening
 
5. Stable dose of insulin (<20% change in units) 6 weeks prior to enrollment
 

Exclusion Criteria:	
1) Sex and Reproductive Status
 
 
a) Women of child-bearing potential who are unwilling or unable to use an acceptable method to avoid pregnancy for the entire study period.
 
b) Women who are pregnant or breastfeeding
 

	
2) Target Disease Exceptions
 
 
a) Gastrointestinal disease (including gastrectomy, chronic pancreatitis, bariatric surgery and gastroparesis)
 
b) Hepatic disease (ALT, AST >2.5 times the upper limit of normal)
 
c) Kidney disease (GFR ≤50 mL/min)
 
d) Hypertension (blood pressure >160/95 mmHg) at screening for the mean of three consecutive readings performed in a sitting position after a 5-minute resting period. If treatment for hypertension has recently
 

	
been initiated, subjects must be clinically stable for 4 weeks prior to screening.
 
 
e) Cardiac disease (myocardial infarction within past 6 months, clinically significant arrhythmia, unstable angina, uncontrolled congestive heart failure, or coronary artery bypass surgery within 1 year or expected to require coronary bypass surgery within 12 months of study entry)
 
 
3) Medical History and Concurrent Diseases
 
 
a) Type 1 diabetes mellitus
 
b) Active malignancy other than basal cell or squamous cell skin cancer (cancers in remission or stable and not receiving active therapy permitted)
 
c) Significant clinical allergic rhinitis or asthma, regularly requiring inhaled corticosteroids and/or antihistamines
 
d) Chronic inflammatory disease (e.g. Rheumatoid arthritis)
 
 
4) Additional Laboratory Test Findings
 
 
a) Hemoglobin <12 g/dl in men, <11 g/dl in women
 
 
5) Allergies and Adverse Drug Reactions
 
History of a serious hypersensitivity reaction to compounds containing lysine, such as anaphylaxis, angioedema, or exfoliative skin conditions.
 
6) Prohibited Treatments and/or Therapies
 
 
a) Regular use of supplements containing lysine, zinc or vitamin C for the last 3 months
 
b) Current or expected treatment with any of the following medications at screening: systemic glucocorticoids (for >2 weeks), antineoplastic agents, transplant medications, drugs for weight loss or anti-retroviral medications
 
c) Treatment with antihistamines or inhaled corticosteroids within 3 months prior to screening
 
d) Start or change of hormonal replacement therapy within 3 months prior to screening
 
 
7) Other Exclusion Criteria
 
 
a) Prisoners, or subjects who are involuntarily incarcerated
 
b) Subjects who are compulsorily detained for treatment of either a psychiatric or physical (e.g., infectious disease) illness
 
c) Currently abusing alcohol or drugs, or have a history of alcohol or drug abuse that in the investigator's opinion could cause the subject to be non-compliant; or have a general history of non-compliance with medications
 
d) Any acute febrile illness within 2 weeks of screening with a temperature <math>\geq 100^{\circ}\text{F}</math>
 


Criteria for Evaluation: Efficacy, safety, stopping rules, etc.)	Study participation will be stopped for adverse effects at the discretion of the study investigator. Subjects may stop study participation at any time and for any reason. Enrollment may be stopped due to futility or efficacy by interim analysis.
Statistical analysis:	A linear mixed effects model will be used to evaluate treatment-induced endpoints. The models will be fit for sequential values of the response variable (including the baseline measurement).
Statistical power:	54 participants will be required to complete the study to detect a of 0.7% points reduction in HbA1c and 19 mg/dl reduction in fasting plasma glucose levels with 80% power at the alpha level of 0.05. This corresponds to SDs for HbA1c 0.9% points and fasting glucose 25 mg/dl.

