Study Visits Schedule: All visits will be performed in the Clinical Research Center (CRC) at the Phoenix VA. Completion of the entire study will involve up 3-4 visits to the CRC. After initial visit for obtaining of informed consent and screening, qualified patients will undergo a baseline testing (on the same day as screening visit or on a separate day), including blood collection for baseline measurements, and will be randomized to treatment (Lysulin™ or matching placebo). Study medication will be dispensed to the subject in a double-blinded fashion by Phoenix VA research pharmacist. Subjects will be instructed to take two tablets orally with breakfast, lunch and dinner. They will return to the CRC for clinical evaluation and blood draws after 6 and 12 weeks (final visit). Subjects will be instructed to not make major lifestyle modifications, including changes to their diet or exercise, during their study participation. At least one phone call contact will take place between interim visits to ensure medication is being taken appropriately and to help address any study related questions. At each visit a comprehensive assessment of side effects, medication compliance/competency and concurrent medical history will be obtained and entered into the database. Additional brief visits may occur as needed to ensure participant comfort/competency with treatment.

Study endpoints:

Primary: Fasting plasma glucose and HbA1c concentrations

Secondary: Fasting plasma AGEs, C-peptide concentrations and lipid measurements

Recruitment Approach: Participants will be recruited utilizing VA electronic medical records to identify potential candidates meeting inclusion criteria, as well as from the Phoenix VA primary care, specialty and women's clinics, community diabetes clinics, ads in VA newsletters and flyers,

permission to be contacted forms, on hold message, social media, clinic list, BISL, list of A1c results from lab, and through VINCI.

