Diabetes care during the study: The research team will provide diet and exercise guidance at baseline and review at subsequent study visits, and monitor side effects, medication changes or general health issues of all subjects. We will notify relevant PCP providers of study activity to avoid unnecessary diabetes medication changes during the study. Addition of diabetes agents will be discouraged, but of course supported if clinically indicated. However, general and diabetes healthcare and routine lab tests will be conducted by the PCP as warranted. With hypoglycemia, excessive hyperglycemia or other adverse events - we will work with the participant and/or primary care team to evaluate/change contributory diet or behavior and/or reduce/modify other diabetes medications as appropriate.

Biochemical analyses: Plasma glucose, HbA1c, creatinine and all safety screening will be measured at the VAMC clinical laboratory using established automated methods. Plasma C-peptide levels will be measured by commercial ELISA kit in the VAMC research laboratory. AGEs will be measured by LC-MS/MS utilizing internal stable heavy isotope substituted standards (Preventage Healthcare technology) if initial data analysis indicates Lysulin had a rapid and favorable effect on HbA1c values.

Data Handling: All participants will be given non-identifying study IDs and all case report forms and samples are labeled with this information. The code for these IDs is stored in locked files in the locked office of the project manager. Only approved VA research employees will have access to study samples and data.

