Statistical Analysis Plan: Univariate numerical and graphical procedures will be used to explore distributional characteristics and dependence structure of measured variables. Data transformations (e.g., logarithm) may be used to improve distributional characteristics and/or to improve linearity of relationships between response and covariates. A linear mixed effects model will be used to evaluate treatment-induced endpoints (glucose, HbA1c, AGEs, C-peptide). This approach allows the inclusion of potential covariates, and explicitly accounts for repeated measurements on each patient (and patient-to-patient variability). We will fit models to all sequential values of the response variable (including the baseline measurement), rather than computing a change score. This structure allows statistically efficient evaluation of treatment effects and allows modeling of differential treatment effects for patients with varying initial glycemic control.

Power Calculation: 54 participants will be required to complete the study to detect a 0.7% points reduction in HbA1c and 19 mg/dl reduction in fasting plasma glucose levels with 80% power at the alpha level of 0.05. This was based on SDs for HbA1c=0.9% points and fasting glucose=25 mg/dl from our previous study in patients with > 5 years duration of type 2 diabetes.

Interim analysis: Using a 2-stage group sequential trial design, an interim analysis will be performed by an independent statistician after completing first 28 participants, i.e. 14 per group. The sample size for interim analyses as well as the boundary values for the treatment effect were computed by SEQDESIGN procedure of SAS v9.4. The SEQTEST procedure will compare the test statistic with the boundary values at the interim stage so that the study can be stopped to reject or accept the null hypothesis. If the interim analysis will indicate futility, the enrollment of new patients will be discontinued. All active participants will complete the study as planned.

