## **Adverse Event Definitions**

Adverse Event (AE): An AE is any undesirable medical event occurring to a subject in a clinical trial, if related to the trial product(s). This includes events reported from the first trial related activity after the subject has signed the informed consent and until post treatment follow-up period as defined in the protocol. The following should not be recorded as AEs, if recorded as medical history/concomitant illness on the CRF at screening:

- Pre-planned procedure, unless the condition for which the procedure was planned has worsened from the first trial related activity after the subject has signed the informed consent
- Pre-existing conditions found because of screening procedures

Clinical Laboratory Adverse Event: A clinical laboratory AE is any clinical laboratory abnormality regarded as clinically significant i.e. an abnormality that suggests a disease and/or organ toxicity and is of a severity, which requires active management, (i.e. change of dose, discontinuation of trial product, more frequent follow-up or diagnostic investigation).

Serious Adverse Event (SAE): A serious AE is an experience that at any dose results in any of the following:

- Death
- A life-threatening\* experience
- In-patient hospitalization or prolongation of existing hospitalization
- A persistent or significant disability/incapacity
- A congenital anomaly/birth defect
- Important medical events that may not result in death, be life-threatening\*, or required hospitalization may be considered an SAE when, based upon appropriate medical judgement, they may jeopardize the subject and may require medical or surgical intervention to prevent one of the outcomes listed in this definition.

Unanticipated (Unexpected) Adverse events: The terms “unanticipated” and “unexpected” refer to an event or problem in VA research that is new or greater than previously known in terms of nature, severity, or frequency, given the procedures described in protocol-related documents and the characteristics of the study population.

Serious unanticipated problems involving risks to subjects or others include:

- (1) Interruptions of subject enrollments or other research activities due to concerns about the safety, rights, or welfare of human research subjects, research staff, or others.

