- (2) Any work-related injury to personnel involved in human research, or any research-related injury to any other person, that requires more than minor medical intervention (i.e., basic first aid), requires extended surveillance of the affected individual(s), or leads to serious complications or death.

Serious Adverse Drug Reaction (SADR): An adverse drug reaction (ADR) is an adverse event for which a causal relationship (Possible/Probable relation) between the study drug and the occurrence of the event is suspected. The ADR should be classified as serious if it meets one or more of the seriousness criteria.

Non-Serious Adverse Event: A non-serious AE is any AE which does not fulfil the definition of an SAE.

Severity Assessment Definitions:

- Mild: Transient symptoms, no interference with the subject’s daily activities
- Moderate: Marked symptoms, moderate interference with the subject’s daily activities
- Severe: Considerable interference with the subject’s daily activities, unacceptable

Related AE or a Related Problem: A “related” AE or a “related” problem in VA research is an AE or problem that may reasonably be regarded as caused by, or probably caused by, the research.

Collection, Recording and Reporting of Adverse Events: All events meeting the definition of an adverse event must be collected and reported from the first trial related activity after the subject has signed the informed consent and until the end of the post-treatment follow-up period as stated in the protocol.

Follow-up of Adverse Events: During and following a subject’s participation in a clinical trial, the sponsor-investigator and institution will provide adequate medical care to the study subject for

any study-related adverse events, including clinically significant laboratory values related to the study as per local VA policy.

All adverse events classified as serious or severe or possibly/probably related to the trial product must be followed until the subject has recovered, is recovering, or the condition has reached a new stable condition, and all queries have been resolved according to local VA policy.

Pregnancy: Study subjects will be instructed to notify the sponsor-investigator immediately if they become pregnant. Pregnancy complications should be recorded as adverse event(s). If the infant has a congenital anomaly/birth defect this must be reported and followed up as a serious adverse event.

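### The plan provides for ending participation after an adverse effect but not for stopping tablets alone, so week-12 primary outcomes are likely to be missing for patients stopped this way

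*Combined protocol and SAP*

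**What the plan says.** The Criteria for Evaluation row of the Protocol Synopsis gives two ways out of the study. One is by the investigator: "Study participation will be stopped for adverse effects at the discretion of the study investigator". The other is by the patient: "Subjects may stop study participation at any time and for any reason". Both end participation; neither is about the tablets alone.

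The endpoints at stake are set out under Study endpoints: "Primary: Fasting plasma glucose and HbA 1c concentrations". Trial Design has both measured at baseline, week 6 and week 12. The Statistical Analysis Plan paragraph fits a linear mixed model to every measured value, baseline included, and says nothing about missing outcomes.

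The sample is planned in completers. The Synopsis accrual goal is "60 subjects for the successful completion of 56 subjects", while the Power Calculation says "54 participants will be required to complete the study".

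Three other places touch on adverse events:

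- The definition of a clinical laboratory adverse event gives examples of active management: "change of dose, discontinuation of trial product, more frequent follow-up or diagnostic investigation".
- Diabetes care during the study lets the team respond to adverse events through diet or behaviour, or "reduce/modify other diabetes medications as appropriate".
- The adverse event follow-up text says that serious, severe or possibly or probably related events "must be followed until the subject has recovered, is recovering, or the condition has reached a new stable condition".

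**The concern.** A site that applies the Synopsis rule as written has no instruction to bring the patient back. Once participation has ended, the week-6 and week-12 visits no longer apply, and no early-termination draw is described. Stopping for an adverse effect can depend on treatment, so the resulting gaps may not be balanced between arms or unrelated to outcome.

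If Lysulin causes some intolerance, its arm would lose patients who had stopped receiving any benefit. Under missing at random, the model in effect fills in their week-12 values from their own earlier measurements and the course of patients who stayed on tablets. The estimate then moves from the effect in everyone randomised towards the effect in those who tolerate the product. A larger sample would not remove this, and samples not drawn cannot be recovered at analysis.

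**Working it through.** **1. Does any section fill the gap?**

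- The laboratory adverse event definition recognises discontinuing the product as an action in its own right, but attaches no rule on outcome collection.
- Adverse event follow-up is for safety and mentions neither HbA1c nor glucose.
- The adverse event text refers to a post-treatment follow-up period defined in the protocol. The available text defines none, and Study Visits Schedule makes week 12 the final visit.
- The Interim analysis paragraph has active participants finish the study, but only when enrolment stops for futility.

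None of these asks a patient who has stopped tablets to return for the primary endpoints.

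**2. Reproducing the plan's sample size.** Inputs from the Power Calculation: HbA1c difference 0.7, SD 0.9; glucose difference 19 mg/dl, SD 25 mg/dl; 80% power; alpha 0.05, taken as two-sided. Normal approximation for HbA1c: n per arm = 2 × (1.960 + 0.842)² × (0.9/0.7)² = 25.95, so 26 per arm. The t-test calculation gives 27 per arm, 54 in total, with power 80.1%. For glucose, power at 54 is 78.3% by the t test and 79.7% by the normal approximation. The figure of 54 reproduces.

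**3. Is power the problem?** Hardly. The margin is 60 − 56 = 4 or 60 − 54 = 6 patients. HbA1c power (t test) is 81.5% at 56 and 80.1% at 54 with balanced losses, and 81.4% and 79.6% if all 4 or 6 losses fall in the Lysulin arm.

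**4. Shift in the estimate.** Assumptions, none of them given in the documents: k of 30 Lysulin patients stop and have no effect at week 12; the rest have the planned effect; placebo stops change nothing; the model returns the on-tablet effect.

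Effect in all randomised = 0.7 × (30 − k)/30. Overstatement = 0.7 × k/30.

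| Stops in Lysulin arm | Effect, all randomised | Overstatement | Relative to that effect |
|---|---|---|---|
| 2 | 0.653 | 0.047 | 7% |
| 3 | 0.630 | 0.070 | 11% |
| 4 | 0.607 | 0.093 | 15% |
| 6 | 0.560 | 0.140 | 25% |

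Two and three correspond to an even split of 4 or 6 non-completers; four and six put all of them in the Lysulin arm. For glucose, 19 × k/30 gives 1.3, 1.9, 2.5 and 3.8 mg/dl. If stopped patients kept half the effect, every overstatement would halve.

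**5. Scale against sampling error.** With 27 per arm the standard error of the HbA1c difference is 0.9 × √(2/27) = 0.245. The overstatement is 0.047/0.245 = 0.19 to 0.070/0.245 = 0.29 standard errors for 2 to 3 stops, and 0.38 to 0.57 for 4 to 6.

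**The case against.** Much can be said for the plan, and several stronger readings fail against it.

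- A reader might infer that any adverse effect ends participation. It does not: the decision is left to the investigator, and Diabetes care during the study offers other responses.
- A reader might infer that week-12 data are lost for exactly the patients who could not tolerate the product. Some patients with adverse effects will stay, and others may leave for unrelated reasons.
- A reader might infer that the primary endpoints are never measured again. No section cancels visits or forbids a final draw; the loss follows from the wording together with silence elsewhere. A patient who stops after week 6 already has a week-6 value. The consent pages are not available, so what patients are told about follow-up cannot be seen.
- A reader might take the completer targets as a sign of a completers-only analysis. They are an ordinary allowance for attrition, and the mixed model keeps every value collected.
- The protocol does not name a treatment-policy target. Against an effect while taking tablets, the figures above would be a difference between two estimands and not bias.
- The background section expects little toxicity, so stops may be few.

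All of this stands and limits the size of the point. It does not supply a rule for collecting outcomes after tablets are stopped, or a sensitivity analysis for departures from missing at random.

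**Conclusion.** The point holds in a limited form. The plan provides only for ending participation, at the investigator's discretion, and makes no provision for week-6 or week-12 primary outcomes once tablets are stopped for an adverse effect. Missing week-12 values in such patients are the likely result, though not a stated one, and the model protects against them only under missing at random.

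The overstatement is about 0.05 to 0.07 HbA1c points (7 to 11%) with 2 to 3 stops in the Lysulin arm. It reaches 0.09 to 0.14 points (15 to 25%) only if all 4 to 6 planned losses are adverse-effect stops in that arm. Both ranges assume that the target is all randomised patients and that stopped patients have no effect at week 12. The upper range should not be read as an expected bias, because the documents give no stopping rate. The matter is worth correcting because the remedy is cheap and works only if adopted before the visits are missed.

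**What to change.** In the Criteria for Evaluation row, and again under Study Visits Schedule:

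- Define stopping the product and leaving the study as two separate events. Leave the decision to stop tablets, and any safety-based decision to end participation, with the investigator.
- State that patients who stop tablets and still consent are asked to attend the scheduled week-6 and week-12 draws for fasting glucose and HbA1c.
- Record the date on which tablets were stopped.

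In the Statistical Analysis Plan paragraph:

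- Name the target effect. If it is the effect in all randomised patients, include values taken after the stop in the mixed model by randomised arm.
- Add a sensitivity analysis for week-12 values that remain missing, for example one that gives stopped Lysulin patients no benefit.

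The cost is a short amendment with consent wording, and at most two already scheduled visits for a few patients. The observed effect will also be somewhat diluted. Under the assumptions above, with all 60 followed, HbA1c power (t test) would be 79% with 2 stops in the Lysulin arm, 76% with 3, 73% with 4 and 66% with 6.
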